**SAMPLE AND DATA COLLECTION.** All participants will collect fecal samples at Days 0, 28, 56, and the day when they recover from COVID-19-like illness (if before Day 56). Participants are considered having recovered from COVID-19-like illness when they fulfil the CDC guidelines for discontinuing home isolation for persons with COVID-19 who have symptoms (updated July 20, 2020): at least 10 days have passed since symptom onset, at least 24 h have passed since resolution of fever without the use of fever-reducing medications, and other symptoms have improved. Participants will be provided with supplies and instructions (Appendices 8.1, 8.2 and 16) to collect fecal samples at home using a collection kit developed by

describe the fecal sample on a data collection form based on the Bristol Stool Scale (Appendix 12) [17] and mail the samples and the form to the research team in a prepaid shipping box by following the written instructions in Appendix 18. For participants who require hospitalization during the study, they will collect a fecal sample after they recover (on or before Day 56) and repeat sample collection on Days 28 and 56 as appropriate.

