All participants will evaluate objective and subjective symptoms, adverse events and medication changes twice a day (in the morning around 8 am and 2 h after dinner around 8 pm using the last 12 h as the recall period) and record fasting blood glucose if participant has T2DM (after at least 8 h of overnight fasting) and consumption of NBT-NM108 (treatment group) or water (control group) once a day from Day 1 to Day 28 or until they recover from COVID-19-like illness (whichever is later) and then once a week until Day 56 (i.e. in the mornings of Days 35, 42, 49 and 56). Participants will also report symptoms, fasting blood glucose if participant has T2DM and medication changes on the day that they recover from COVID-19like illness (if before Day 56). For measurement of body temperature (oral), oxygen saturation level, pulse rate and respiratory rate and fasting blood glucose if participant has T2DM, participants will be provided with devices and instructions to take the measurements; for the remaining subjective symptoms, participants will be asked to evaluate the severity of each symptom using categorical options of "none", "mild", "moderate", and "severe" or the severity of the symptoms as directed. Participants will be asked to record these data and any adverse events in the participant booklet (Appendices 8.1 and 8.2) and report to the research team on Castor (Appendices 9-11). For participants who are hospitalized during the study, they will stop collecting data themselves during hospitalization but body temperature (oral), pulse rate, respiratory rate, oxygen saturation level, fasting blood glucose if participant has T2DM, respiratory support and other data related to the clinical progress of COVID-19-like illness will be extracted from their medical records at the hospital. If these patients are discharged on or before Day 56, they will collect data on objective and subjective symptoms and medication changes twice a day and fasting blood glucose if

Protocol Title: COVGUT20

participant has T2DM once a day after they are discharged until they recover from COVID-19-like illness and once a week thereafter until Day 56.

Medical history and regular medications will be extracted from the primary care medical records. If participants are hospitalized during the study, clinical data related to COVID-19-like illness will be extracted from the hospital medical records.

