## D. Endpoints

- 1. Primary outcome:
  - Gut microbiota composition
- 2. Secondary outcomes:
  - At Days 1, 14, 28 and 56:
  - a) Outcome of COVID-19-like illness (hospitalization or death)
  - b) Proportion of participants who are "alive and not admitted to the hospital"
  - c) Proportion of participants who visit the emergency room
  - d) Proportion of participants who have complete resolution of all objective symptoms, i.e. all vital signs are within the normal range for at least 48 h, including body temperature (oral) 36.5-37.5°C (97.7-99.5°F), pulse rate 60-100/min, respiratory rate 12-20/min and oxygen saturation level at 95-100%
  - e) Proportion of participants who have complete resolution of subjective symptoms, i.e. absence of all COVID-19-like symptoms listed by CDC (updated May 13, 2020) for at least 48 h, including the presence of chills or "feeling feverish", cough, shortness of breath or difficulty breathing, fatigue, muscle or body aches, headache, new loss of taste or smell, sore throat, congestion or runny nose, nausea or vomiting and diarrhea
  - f) Proportion of participants who have complete resolution of subjective symptoms except fatigue and cough, i.e. absence of all COVID-19-like symptoms listed by CDC (updated May 13, 2020) for at least 48 h, including the presence of chills or "feeling feverish", cough, shortness of breath or difficulty breathing, fatigue, muscle or body aches, headache, new loss of taste or smell, sore throat, congestion or runny nose, nausea or vomiting and diarrhea
  - g) Illness severity based on the categorization from FDA [18] and the Ordinal Scale for Clinical Improvement from the World Health Organization [19]
  - h) Body temperature (oral)
  - i) Oxygen saturation level
  - i) Pulse rate
  - k) Respiratory rate
  - I) Fasting blood glucose
  - Time to complete resolution of all objective symptoms
  - Time to complete resolution of all subjective symptoms
  - Time to complete resolution of all subjective symptoms except fatigue and cough

Protocol Title: COVGUT20

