# C. Subject Screening

# Inclusion Criteria

- Aged between 18 to 79 (inclusive)
- Have mild to moderate COVID-19-like symptoms based on the symptom list from CDC (updated May 13, 2020) and the severity categorization from FDA [18]:
  - a) Mild COVID-19

- Fever or chills, cough, shortness of breath or difficulty breathing, fatigue, muscle or body aches, headache, new loss of taste or smell, sore throat, congestion or runny nose, nausea or vomiting, and diarrhea
- · No clinical signs indicative of moderate, severe, or critical illness severity
- b) Moderate COVID-19
  - Symptoms of moderate illness with COVID-19 could include any symptom of mild illness or shortness of breath with exertion
  - Clinical signs suggestive of moderate illness with COVID-19, such as respiratory rate ≥ 20 breaths/min, oxygen saturation level > 93% on room air at sea level, heart rate ≥ 90 beats/min
  - No clinical signs indicative of severe or critical illness severity.
- Directed to home isolation by study physician

\_

- Practice acceptable contraception, i.e., continue with current methods if participants are already
  practicing contraception, otherwise parti cipants must agree to practicing contraception with a
  barrier method (male or female condom) or abstinence, from Day 1 to Day 35 or 7 days after the
  last dose of NBT-NM108 if they do not complete the 28-day intervention.
- Have access to a smartphone, tablet, computer, or other qualifying internet-enabled device and daily internet access
- Understand and be able to follow written and oral instructions in English
- Provide informed consent

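### Endpoint (d), resolution of objective symptoms, sets no condition on respiratory support, admission or fever-reducing drugs, so supported or medicated vital signs can count as complete resolution

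*Protocol*

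**What the plan says.** Endpoint (d) (Protocol 1.3 D) is met when "all vital signs are within the normal range for at least 48 h". The ranges are "body temperature (oral) 36.5-37.5°C (97.7-99.5°F"), pulse 60 to 100 per minute, and "respiratory rate 12-20/min and oxygen saturation level at 95-100" per cent. It is reported as a proportion at Days 1, 14, 28 and 56. A separate secondary outcome is the time until objective symptoms have completely resolved.

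Two other places read the same signs with a condition attached. The recovery definition (1.3 A, Sample and Data Collection) requires that "at least 24 h have passed since resolution of fever without the use of fever-reducing medications". The moderate-illness entry criterion (4.1 C) refers to "oxygen saturation level > 93% on room air at sea level".

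For admitted participants, section 1.3 A says that "they will stop collecting data themselves during hospitalization but body temperature (oral), pulse rate, respiratory rate, oxygen saturation level" and fasting glucose are taken from the hospital record, and that "respiratory support and other data related to the clinical progress of COVID-19-like illness will be extracted from their medical records at the hospital". For participants at home, "All participants will evaluate objective and subjective symptoms, adverse events and medication changes twice a day".

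The analysis text (Protocol 6.1; SAP, Clinical Data Analysis) compares the proportions by logistic regression at each time point. It compares the times by competing-risks methods, naming death or self-reported illness severity as the competing risk.

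**The concern.** A vital sign measured under support shows the effect of the support as well as the state of the illness. As defined, (d) cannot separate a participant whose signs became normal unaided from one whose saturation is maintained by oxygen or whose temperature is held down by medication. Admission could even help a participant meet the endpoint, which runs against the trial's hypothesis of reduced illness severity.

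The control group drinks plain water, so participants can know their arm. If fever reducers are used more in one arm than the other, (d) and its time-to-event version could differ between arms without any difference in disease.

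**Working it through.** There is no stated figure to reproduce: the documents give no expected rate, event count or power for (d). The check is a comparison of texts, followed by applying the rule as written.

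**1. Does any text supply the missing conditions?**

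| Place | Content relevant to (d) | Condition on support, admission or antipyretics |
|---|---|---|
| Protocol 1.3 D, endpoint (d) | Four ranges, 48 h | None |
| Protocol 1.3 D, time to resolution | No further definition | None |
| Protocol 1.3 B, Data Points | Symptom collection schedule | None |
| Protocol 1.6 B, Outcome Measures | Repeats the outcome names | None |
| Protocol 1.9 A, Timing and Frequency | Hospital data retrieved from records | None |
| Protocol 6.1 and SAP, Clinical Data Analysis | Logistic, log-rank and competing-risks analyses | None for (d) |
| Protocol 1.3 A, recovery | Fever resolution | No fever-reducing medication |
| Protocol 4.1 C, moderate illness | Saturation | Room air |

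The two places that state a condition concern recovery and eligibility. Nothing links either to (d).

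**2. Apply (d) as written.**

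- *Inpatient on supplemental oxygen.* Suppose saturation is 97%, temperature 37.0°C, pulse 88 and respiratory rate 16 for 48 h. Then 95 ≤ 97 ≤ 100, 36.5 ≤ 37.0 ≤ 37.5, 60 ≤ 88 ≤ 100 and 12 ≤ 16 ≤ 20. Endpoint (d) is met. On the same day the participant fails endpoint (b), being alive and not admitted.
- *Participant at home taking an antipyretic.* With the same four readings, (d) is met, but the fever part of the recovery definition is not.
- *Participant above 37.5°C despite an antipyretic.* Endpoint (d) is not met. The rule therefore can, but need not, score a treated participant as resolved.

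**3. Does the analysis correct this?** The named competing risk does not include hospitalization or oxygen use, and admitted participants stop recording data themselves. In the time-to-event analysis, the first qualifying 48 h window counts as the event, so an admission that falls between scheduled days can also generate one. The logistic regressions have no scoring rule for admitted or medicated participants.

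**4. Size.** With 100 participants randomized 1:1 (Protocol 1.5), there are 50 per group, and one participant is 1/50 = 2 percentage points. A net imbalance of k misclassified participants shifts the difference between groups by 2k points: 2 points for k = 1, 10 points for k = 5.

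The rates needed to predict k are not in the documents. If 5 to 10% were admitted (an assumption), that would be 5 to 10 participants across both groups. This is a ceiling for the admission route, because each must also have all four signs in range on support for 48 h. If 30 to 60% of febrile participants used fever reducers (also an assumption), no count follows, because fever is not required at entry and the number febrile is not given.

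**The case against.** The best defence is that the trial would not hide a bad outcome. Hospitalization is reported in endpoints (a) and (b), severity in (g), and time to hospitalization is analysed. Time to recovery, whose definition already excludes fever reducers, is compared as well. This stands as a limit on the consequences: a reader of the full results would see the admissions. It does not repair (d), because none of these outcomes enters its definition or its analysis.

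A second defence is that the contrast within the Protocol is weaker than it looks. The room-air wording belongs to one entry criterion for outpatients, the recovery rule is an isolation guideline, and the saturation threshold among the red flags in section 4.7 E has no room-air qualifier. This is fair. The Protocol does not state a general rule that these signs count only when unsupported; it does so in two places and leaves (d) silent.

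Two stronger inferences should be resisted. A reader might conclude that anyone on oxygen or antipyretics is scored as resolved. That fails, because all four signs must stay in range for 48 h. A reader might also conclude that inpatients' subjective symptoms are never collected, so that the sickest participants drop out of (e) and (f). The inpatient list does not name subjective symptoms, but it includes other data on clinical progress, and section 1.3 B defines clinical progress to include them. Missing data is not established. Multiple imputation is also planned as a sensitivity analysis.

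Finally, the participant forms and booklets (Appendices 8.1, 8.2 and 9 to 11) are not available here and could carry measurement instructions. Nothing in the available text points to such a rule for (d).

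**Conclusion.** The point holds for (d) and for the time to resolution of objective symptoms. Both lack any condition on respiratory support, hospitalization or fever-reducing medication, so a supported inpatient or a medicated participant can be counted as completely resolved. The mechanism follows from the text alone. Its size does not: the documents give no rates of admission, oxygen use or antipyretic use, so only the scale of 2 percentage points per misclassified participant is firm.

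The effect is confined to secondary outcomes in a trial that describes itself as a feasibility study. The primary microbiota outcome and the sample size in Protocol 1.5 are untouched. The definition should still be corrected before the analysis.

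**What to change.** In (d) and its time-to-event version, require that the participant is alive, not hospitalized and on room air throughout the 48 h window. Score anyone dead or hospitalized on an assessment day as not resolved. For consistency, use the same dead-or-hospitalized scoring in (e) and (f), and carry the wording into Protocol 6.1 and the SAP.

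For temperature, choose one of two options in advance:

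- Require no fever-reducing medication across the same 48 h. Borrowing the recovery rule's 24 h would leave 48 − 24 = 24 h of the window uncovered.
- Keep the main definition free of this condition and report the antipyretic-free version as a prespecified sensitivity analysis. This option has merit because the same drugs are taken for pain, and the first option would score an afebrile participant as unresolved for treating a headache.

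The cost is mainly wording. Admission status and inpatient respiratory support are already collected, and medication changes are reported twice daily up to Day 28 or recovery, whichever is later. Two checks on the forms are needed: that as-needed antipyretics are captured, and that oxygen use after discharge is captured, since respiratory support is named only for hospital records. Diaries then become weekly, so the SAP should say how a 48 h condition is judged at Day 56.

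The price is later resolution times and somewhat lower proportions resolved. Scoring admission as non-resolution also makes (d) to (f) overlap with (b), and the SAP should say so. The change affects scoring only, not participants' care.

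### Subjective symptom resolution requires absence of 11 symptoms with almost no allowance for the participant's usual state, so persistent pre-illness symptoms dilute these secondary analyses

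*Protocol*

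**What the plan says.** Protocol section 1.3 D lists symptom resolution among the secondary outcomes; the primary outcome is "Gut microbiota composition". Endpoint (e) needs "absence of all COVID-19-like symptoms listed by CDC (updated May 13, 2020) for at least 48 h". The list that follows has 11 items: chills or feverishness, cough, breathlessness, fatigue, aches, headache, taste or smell loss, sore throat, congestion, nausea or vomiting, and diarrhea. One item is worded against the prior state: "new loss of taste or smell".

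Endpoint (f) is titled "Proportion of participants who have complete resolution of subjective symptoms except fatigue and cough". Its explanatory text then repeats the list from (e), with fatigue and cough still in it. The time-to versions include "Time to complete resolution of all subjective symptoms except fatigue and cough".

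In the diary, "participants will be asked to evaluate the severity of each symptom using categorical options" from none to severe, or as directed (Protocol 1.3 A). No usual-level anchor is described. Recovery is defined separately and more loosely: "at least 24 h have passed since resolution of fever without the use of fever-reducing medications, and other symptoms have improved".

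Eligibility (Protocol 4.1 C) admits ages 18 to 79. It excludes certain chronic bowel diseases, but not chronic cough, headache, fatigue or congestion. Medical history is collected, but no section describes recording the pre-illness level of each symptom.

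Protocol 6.1 and the SAP's Clinical Data Analysis section compare resolution times by Gray's test and Fine-Gray regression. They also plan survival analysis without competing risks, and logistic regression of the proportions at each time point.

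**The concern.** For 10 of the 11 items the definition does not separate a symptom of this illness from one the participant already had. A person who has returned to normal but has mild congestion every day is scored unresolved to the end of follow-up.

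Such people should be equally common in both arms, so the type I error is not affected. The harm is dilution. If treatment speeds resolution, the treated arm empties of resolvable participants sooner. Its late risk set then consists mostly of people who cannot have the event, and the observed hazard ratio drifts towards 1 and below it. The Day 28 and Day 56 proportions also cannot exceed 1 minus the affected share.

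What is at stake is the information these secondary endpoints can give on the effectiveness part of the objective (Protocol 1.1 A) with only 100 participants.

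**Working it through.** **The plan's own figure.** Protocol 1.5 gives 16 per group for 80% power by PERMANOVA on the microbiota endpoint. It cannot be reproduced, because the within-group distance mean and standard deviation are unpublished. The arithmetic around it is sound: 50 × 0.40 = 20 confirmed cases per group, and 16/(1 − 0.20) = 20. No power, event count or effect size is given for any symptom endpoint.

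**Inputs from the documents.** 50 per group, p < 0.05 (two-sided assumed), follow-up to Day 56.

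**Assumptions, not in the documents.** Exponential times to resolution, control median 10, 14 or 21 days, hazard ratio (HR) 1.75, no competing events, and a share f in each arm who cannot meet the definition (0, 5, 10 or 20%).

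**Step 1: lost events only.** Power = Φ(√d × ln HR / 2 − 1.96). If 95% of the others resolve, d = 95(1 − f) and ln 1.75 / 2 = 0.2798.
- f = 0: d = 95; 9.747 × 0.2798 − 1.96 = 0.77; power 0.78.
- f = 20%: d = 76; 8.718 × 0.2798 − 1.96 = 0.48; power 0.68.

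Counting lost events alone therefore shows only mild erosion.

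**Step 2: drift of the hazard ratio.** The resolvable fraction of an arm's risk set at time t is (1 − f)S(t) / [f + (1 − f)S(t)]. The observed ratio is 1.75 times treated fraction over control fraction. Take f = 10% and control median 10 days.
- Day 14: control S = 2^−1.4 = 0.379, fraction 0.341/0.441 = 0.773. Treated S = 2^−2.45 = 0.183, fraction 0.165/0.265 = 0.622. Ratio 1.75 × 0.622/0.773 = 1.41.
- Day 28: control S = 2^−2.8 = 0.144, fraction 0.129/0.229 = 0.564. Treated S = 2^−4.9 = 0.0335, fraction 0.0301/0.1301 = 0.232. Ratio 1.75 × 0.232/0.564 = 0.72.

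Late events thus count against the treated arm, which step 1 misses.

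**Step 3: simulated log-rank power**, HR 1.75, 50 per arm, 1,500 runs per cell (95% simulation error at most 1.96 × √(0.25/1500) = 0.025).

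| Control median, censoring | f = 0 | 5% | 10% | 20% |
|---|---|---|---|---|
| 10 days, Day 28 | 0.73 | 0.61 | 0.46 | 0.30 |
| 14 days, Day 28 | 0.73 | 0.61 | 0.55 | 0.36 |
| 21 days, Day 28 | 0.64 | 0.58 | 0.53 | 0.40 |
| 10 days, Day 56 | 0.78 | 0.50 | 0.36 | 0.19 |
| 21 days, Day 56 | 0.76 | 0.63 | 0.49 | 0.34 |

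Within simulation error these are the ranges 0.65-0.78, 0.50-0.62, 0.37-0.54 and 0.20-0.39. The loss at 5% runs from 0.06 (0.64 to 0.58) to 0.28 (0.78 to 0.50).

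**Step 4: other effect sizes** (4,000 runs, Day 56, medians 10 to 21 days; f = 0, 5, 10, 20%).
- HR 2.0: 0.90-0.93, 0.66-0.78, 0.47-0.65, 0.27-0.45.
- HR 1.5: 0.49-0.51, 0.31-0.38, 0.22-0.30, 0.13-0.21.

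**Step 5: proportions.** The ceiling is 1 − f, that is 95%, 90% and 80%. Any difference in proportions resolved shrinks by the same factor.

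**The case against.** A reader might infer that people with chronic cough, fatigue, headache or congestion can never resolve, and that log-rank power collapses. The documents do not support that.

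- One symptom-free 48 h window is enough, so intermittent symptoms can qualify.
- Endpoint (f) is plainly intended to set fatigue and cough aside. That relief is uncertain only because its text contradicts its title, and it does not reach headache, congestion, aches or breathlessness.
- The log-rank test is named for death and recovery. Gray's test and Fine-Gray regression are named for resolution time. Gray's test reduces to the log-rank test when there are no competing events, so a similar loss applies, but the log-rank figures are only an illustration.
- The largest losses come from a short median with full observation to Day 56. After Day 28, a participant who already meets the looser recovery rule gives one morning entry a week with 12 h recall, which cannot establish 48 h of absence. For such people the Day 28 figures are the nearer guide.
- The endpoints are secondary and unpowered. At HR 1.5, power is only about 0.5 even when nobody is affected, so the definition is not the only limit.
- The booklet and diary forms (Appendices 8.1, 8.2 and 9-11) were not available, so an instruction to rate symptoms against the usual state cannot be ruled out.

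These points limit the size of the effect. They do not remove the gap, because the endpoint as written says absence. Strict absence is a defensible choice for a sensitivity analysis, but as the sole rule it scores some people who are back to normal as failures.

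**Conclusion.** The point holds in a limited form. For 10 of 11 symptoms, endpoint (e) and its time-to version make no allowance for a persistent pre-illness symptom. Endpoint (f) and its time-to version share the problem for at least the symptoms other than fatigue and cough. Read literally, (f) is identical to (e).

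The consequence is dilution without arm bias in the Gray, Fine-Gray, Cox and non-competing-risk analyses, plus a ceiling on the later proportions. Under the stated assumptions the power loss is modest to substantial at a 5% share and large at 20%. The share, the medians and the hazard ratio are all assumed, since the documents give none of them. The microbiota endpoint and its sample-size statement are unaffected. The change is worth making because it is cheap and because a usual level cannot be recovered reliably later.

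**What to change.** 1. At the screening interview, before randomization, record the usual pre-illness level of each of the 11 symptoms on the none/mild/moderate/severe scale. The first diary entry is too late: it follows allocation, and with plain water as control participants know their arm and could influence their own threshold.
2. In Protocol 1.3 D, define resolution in (e), (f) and both time-to versions as each symptom absent or back to its recorded usual level for at least 48 h. Carry the same definition into Protocol 6.1 and the SAP.
3. Keep strict absence as a sensitivity analysis.
4. Reconcile the explanatory text of (f) with its title.

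The cost is 11 one-time items in the screening form and a short edit to the endpoint definitions. The downside is that the usual level is recalled by the participant; recording it before allocation keeps that error independent of arm.
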